7.7 End of the clinical trial

7.7.1 Scheduled end

The scheduled end of the clinical trial is defined as the date on which all follow-up data have been recorded and monitored in the eCRF. According to GCP-V § 13 (30), the sponsor will inform the competent authority, the competent higher federal authority and the responsible ethics committee within 90 days of the termination of the clinical trial. Within one year of completion of the clinical trial, the sponsor will submit a summary report of the clinical trial covering all results of the clinical trial to the competent higher federal authority and the relevant ethics committee.

7.7.2 Premature termination of the trial in a trial centre

The SpB will decide on the interruption or termination of the clinical trial in a trial centre, possibly in coordination with the Safety Committee and the biometrician.

The clinical trial may be discontinued or terminated at a trial centre if

- the trial centre does not meet the technical requirements specified in the study protocol,
- the procedures related to the clinical trial do not comply with the protocol,
- there are serious, unexplained problems with the quality of the collected data (insufficient quality of data),
- the recruitment rate in the trial centre is inadequate,
- unpredictable circumstances have occurred in the respective trial centre that do not allow continuation of the clinical trial (e.g., lack of personnel and equipment capacity, the required logistics can no longer be applied)

If there are ethical concerns about the continuation of the clinical trial by an investigator. deputy, or a medical member of the trial group, this must be reported immediately to the SpB. If termination of the clinical trial in a trial centre is initiated by the trial centre itself, the latter must give written reasons for this decision.

Investigators, deputies, or members of the trial group at a trial centre who are no longer participating in the clinical trial must inform SpB immediately about their decision. The decision must be justified.

It is the responsibility of the investigators and the SpB to comply with the disclosure, documentation and notification requirements of GCP-V (30).

In the event that a trial centre has to be closed prematurely, a final visit will be made by the trial monitor. Details are described in the Monitoring Manual.

7.7.3 Premature termination of the entire clinical trial

The SpB is entitled to interrupt or prematurely terminate the clinical trial for relevant medical and administrative causes. Any interruption or premature termination of the entire clinical trial should be discussed in advance with the SMC. The reasons for interrupting or terminating the trial should be documented in detail.

The SpB is entitled to suspend or terminate the entire clinical trial if:

- the recruitment rate is inadequate,
- there are serious, unexplained problems with the quality of the collected data,
- unacceptable risks have arisen (decision after new benefit-risk assessment),
- new scientific evidence does not allow continuation of the clinical trial during the clinical trial period, or
- a risk to patient safety emerges.

Since the clinical trial is carried out in accordance with the provisions of the German Medicinal Products Act, the responsible BOB can also revoke the license or cancel it.

The trial procedures for all patients whose participation in the clinical trial has not yet ended must be determined.

The participant must be informed immediately of any interruption or early termination of the trial. Appropriate further treatment or follow-up must be guaranteed. The date and reason for the interruption or premature termination must be documented.

The data available until early termination must be evaluated and a final clinical trial report must be prepared. If clinical examination is discontinued or interrupted by the SpB, the trial centres should be informed. In accordance with GCP-V § 13 (8) (30), the SpB should inform the competent state authority, the competent BOB and the responsible ethics committee within 15 days, stating the reasons for the termination or interruption of the trial. It is the responsibility of the investigators and the SpB to comply with the duties of disclosure, documentation and notification under GCP-V.

Details of the final visit of the trial monitor in the trial centres are described in the Monitoring Manual.

8. Safety and adverse events

KLINIKUM

8.1 Assessment of the safety of the trial drug

The trial drug contains human albumin as an active substance. Human albumin is a normal component of human blood plasma and does not differ in its effects from physiological albumin. According to the valid information brochure, there are only a few rare or very rare adverse effects. Data on safety and compatibility are described in the valid information brochure. For the clinical trial, safe application can be assumed. Safety management will ensure patient safety for the clinical trial. In addition, adverse events observed during the clinical trial will be recorded, evaluated, and regularly reviewed by an independent safety committee.

8.2 Adverse events

According to GCP-V § 3 (30), an Adverse Event (AE) is any unfavourable event that occurs to a patient participating in a clinical trial who has received an investigational medicinal product and that is not necessarily causally related to the treatment. According to ICH-GCP (29), these may be symptoms (including, for example, abnormal laboratory values), diseases or signs that are associated with the use of an investigational medicinal product. This is independent of whether the event is causally related to the investigational product or not. For the ARISS study, assessment of adverse events will also be done in patients of the control group without albumin.

Septic shock, which is the basic inclusion criterion of this clinical trial in all study patients, is one of the most life-threatening clinical pictures. The ICU mortality from severe sepsis and septic shock is 47% according to the prevalence study of the sepsis competence network (7). Many of the patients need mechanical ventilation and about half the patients have acute kidney failure. Hepatic and metabolic parameters are almost always altered depending on the severity of sepsis. Previous studies investigating severe sepsis or septic shock, such as MAXSEP (EudraCT 2006-006984-21) and SISPCT (EudraCT 2007-004333-42), have therefore performed selective AE evaluation that has been shown to be reliable and which should also be used in the ARISS study.

Because most septic patients have altered laboratory values and symptoms because of the underlying disease and are constantly evolving as the disease progresses, the definition of AE is restricted as follows in this clinical trial:

An adverse event in the ARISS is any adverse event that occurs to a study subject that is not necessarily causally related to the trial drug. If an adverse event can be explained by the underlying sepsis, the following applies:

Events plausibly explainable by sepsis are recorded in both groups as sepsis-related clinical events in the daily eCRF visits, but not as AEs. This rule concerns the following clinical events:

- Death caused by severe sepsis or septic shock
- Cardiovascular event requiring the administration of vasoactive substances
- Respiratory event: e.g., decrease in PaO2/FiO2 ratio, hypoxia, ARDS, acute pulmonary dysfunction, and mechanical ventilation
- Hepatic event: e.g., Liver failure or liver dysfunction
- Renal event: e.g., Kidney failure, renal insufficiency
- Haematological event: e.g., coagulopathy, DIC, thrombocytopaenia, thrombocytosis
- Neurological event: e.g., delirium, confusion

Each sepsis-related clinical event must be documented in the eCRF during the respective visit with specific parameters. The investigator assesses the sepsis-related clinical event in ZKSJ0112 ARISS

Zentrum für Klinische Studien

terms of an association with the trial drug and classifies it as "possible" or "not possible". Documentation of the sepsis-related clinical event as an AE occurs only if the examiner suspects a connection with the administration of the trial drug, which is therefore only possible in the albumin group.

However, the following effects of the trial drug may be substance-specific and must be documented as AE:

- Flush
- Urticaria
- Fever
- Nausea
- Anaphylactic shock
- Hypervolaemia
- Pulmonary oedema
- Transmission of infection (in addition to sepsis, see corresponding section of the valid information brochure).

Clinically relevant worsening of a pre-existing disease not related to sepsis should be considered and documented as an AE.

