5.1.2 Inclusion criteria

Patients who meet all the following inclusion criteria may be included in this clinical trial:

- Presence of septic shock that meets all the following criteria (1):
 - o Clinically possible, probable or microbiologically confirmed infection according to the definitions of the International-Sepsis-Forums (ISF) (2)
 - o Despite adequate volume therapy, vasopressors are required to maintain mean arterial pressure (MAP) \geq 65 mm Hg for at least 1 hour
 - o Serum lactate concentration > 2 mmol/l (18 mg/dl) despite adequate volume therapy
- Onset of septic shock less than 24 hours prior to study inclusion, so that administration of the initial dose of the trial product is possible within 6-24 hours after the onset of septic shock in the albumin group
- Age: ≥ 18 years
- Written informed consent of the patient or his/her legal representative (guardian) or confirmation of the urgency of participation in the clinical trial and the possible benefit to the patient by an independent consultant or the implementation of other established procedures according to the local regulations of the contributing centre to include patients who are unable to provide informed consent in whom subsequent consent may be obtained retrospectively (for more details see chapter 5.2)
- Patient of childbearing age: negative pregnancy test

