8.3 Duration of recording adverse events

Recording of AEs and sepsis-related adverse events begins at randomisation. Because the study drug is human albumin, which is a normal constituent of human blood plasma, and does not differ in its effects from physiologic albumin, recording and follow-up of AEs and SAEs for a maximum of 24 hours after the last dose of the trial drug is considered to be sufficient. Therefore, AEs and sepsis-related adverse events will be recorded

- in the albumin group until 24 h after the last dose of the trial drug and
- in the control group without albumin until day 28 after randomisation or until discharge from the ICU, if it occurs before day 28 after randomisation.

In the event that AEs or SAEs are still "ongoing" after the above dates, they will be tracked until maximum the end of data collection (Day 90). If they are "ongoing" on day 90, they are documented as "not recovered," "recovered with sequelae," or "unknown."

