6.8 Safety and Tolerability Analyses

6.8.1 Adverse Events

For sepsis related AEs, frequency analysis with respect to categories cardiovascular / respiratory / hepatic / renal / hematological / neurological, will be presented.

Respective entries of AEs possibly related to study medication in AE data base will be selected and presented separately.

All AEs and serious AEs will be presented by incidence analysis of the pre-specified categories as well as intensity, relationship to study medication, measures with respect to study medication as well as other measures and outcome. Events of category "Other" will be listed.

For infections, frequency analysis over types, grade and origin will be provided. Analysis of daily assessed data will be performed over the following time frames: Screening / 6h after randomization / Day 1 / Day 2-7 / Day 8-28.

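### The sepsis-related event table mixes organ dysfunction present at entry with new events: every patient meets the cardiovascular definition at inclusion, and the other rows are diluted by existing disease

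*Protocol*

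**What the plan says.** Protocol 5.1.2 requires septic shock in which "Despite adequate volume therapy, vasopressors are required to maintain mean arterial pressure (MAP"; the criterion goes on to name a pressure threshold and a duration of at least one hour.

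Protocol 8.2 takes events plausibly explained by sepsis out of the AE section and records them at the daily visits in both arms. The cardiovascular category is "Cardiovascular event requiring the administration of vasoactive substances". The respiratory one is "Respiratory event: e.g., decrease in PaO2/FiO2 ratio, hypoxia, ARDS, acute pulmonary dysfunction, and mechanical ventilation". Renal, hepatic, haematological and neurological categories are given by example. Such an event becomes an AE only if the investigator suspects the trial drug, which the protocol notes can happen only in the albumin group.

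Protocol 8.3 states: "Recording of AEs and sepsis-related adverse events begins at randomisation". SAP 6.8.1 then plans: "For sepsis related AEs, frequency analysis with respect to categories cardiovascular / respiratory / hepatic / renal / hematological / neurological, will be presented". SAP 6.2 has all analyses shown by treatment group and in total.

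On how common these states are, Protocol 8.2 says: "Many of the patients need mechanical ventilation and about half the patients have acute kidney failure". It adds: "Hepatic and metabolic parameters are almost always altered depending on the severity of sepsis".

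**The concern.** A safety comparison of organ events should show what happened after randomisation that was not there before. Here the categories are largely described as states. Only parts of the respiratory wording (a fall in the oxygenation ratio, acute dysfunction) imply change. A patient admitted on vasopressors, ventilated and in renal failure can be counted in three rows before albumin has had any effect.

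The Synopsis names sepsis-related clinical events among the safety endpoints. The AE section cannot give a like-for-like comparison of them, because only albumin patients can have such an event moved into it. If the two-arm table mainly reflects baseline disease, an excess of new organ dysfunction under albumin could pass as similar rates in both arms.

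**Working it through.** **Arm size.** Protocol 11.1 gives 706 evaluable patients per arm for 50% against 42.5% mortality (two-sided 0.05, 80% power). The two-proportion formula gives 693 per arm uncorrected and 719 with continuity correction, and 706 per arm has 80.7% power. The figure reproduces and serves below only as the arm size.

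**Model.** Let b be the share of patients already in a category at entry and r the rate of new onset among the rest. An ever/never table shows

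E = b + (1 − b) × r,

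so the difference between arms is (1 − b) × (r_albumin − r_control). Power uses the normal approximation with pooled variance under the null:

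Power = Φ{ [d − 1.96 × √(2p̄(1 − p̄)/n)] / √([p₁(1 − p₁) + p₂(1 − p₂)]/n) }.

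**Cardiovascular.** Eligibility sets b = 1, so E = 1 + 0 × r = 100% in each arm for any r. Nobody is at risk of a first event.

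**Renal.** Take b = 0.5 from Protocol 8.2. That figure describes the patient population, so its use as entry prevalence is an assumption. Assume r = 30% (control) and 40% (albumin).
- Planned table, n = 706: 0.5 + 0.5 × 0.30 = 65% and 0.5 + 0.5 × 0.40 = 70%. Power = Φ[(0.05 − 1.96 × 0.0249)/0.0249] = Φ(0.046) = 52%.
- At-risk table, n = 353: 30% against 40%. Power = Φ[(0.10 − 1.96 × 0.0359)/0.0357] = Φ(0.83) = 80%.

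**The other four categories.** No entry percentage is given, so the range is shown with the same assumed onset rates:

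| Entry prevalence | Planned table, control vs albumin | Power | At risk per arm | Power at risk |
|---|---|---|---|---|
| 25% | 47.5% vs 55% | 81% | 530 | 93% |
| 50% | 65% vs 70% | 52% | 353 | 80% |
| 75% | 82.5% vs 85% | 25% | 176 | 50% |
| 90% | 93% vs 94% | 12% | 71 | 24% |
| 95% | 96.5% vs 97% | 8% | 35 | 14% |

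At high entry prevalence the at-risk table is also weak, because few patients remain in it. An onset rule alone is therefore not enough, and patients already affected need a worsening rule.

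**Does the SOFA analysis fill the gap?** Protocol 11.3.2 defines organ failure by onset, a rise from below 2 to 2 or more, with Kaplan-Meier for the first failure. SAP 6.7 counts any subscore above 2 (dysfunction) or above 3 (failure) without reference to baseline. In the appendix SOFA table, adrenaline or noradrenaline scores 3 or 4, so a patient on either drug at entry already exceeds the SAP's dysfunction cut. SAP 6.11, which lists deviations from the protocol, does not mention this change.

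**Observation period.** Under Protocol 8.3 these events are recorded until 24 h after the last dose in the albumin arm, but until day 28 or ICU discharge in the control arm. The daily visits in Protocol 7.5 run in both arms for as long as the patient is in the ICU, up to day 28.

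**The case against.** A reader might infer that all six rows start at or near 100% and that the table cannot show harm at all. The documents do not support that. Full prevalence at entry is established for the cardiovascular category only. Kidney failure is put at about half, and ventilation is said only to be needed by many. Altered hepatic parameters are not a rate of liver failure, and nothing is given for haematological or neurological events. A contrast of 65% against 70% is diluted but visible.

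A reader might also infer that this table is the only record of organ harm. It is not. Protocol 8.2 requires hypervolaemia and pulmonary oedema to be documented as AEs, so the most direct signs of fluid overload are captured elsewhere. SOFA over time, vasopressor- and ventilator-free days, laboratory values and renal replacement are reported by arm, and SAP 5.3 compares baseline SOFA with treatment days. These stand as partial safeguards, but none is a planned by-arm count of new or worsened events for each organ category.

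SAP 6.8.1 also splits daily data into Screening, 6 h, Day 1, Day 2-7 and Day 8-28. If this applies to these events, the later windows can fall below 100% even for the cardiovascular row. They would still pool persistent with new dysfunction. Because recording begins at randomisation, the Screening window may hold no event data to serve as baseline.

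Finally, Protocol 8.4 leaves out illnesses present before consent and normal progression of sepsis. That rule is written for AEs, but the documents sometimes call sepsis-related events AEs, so its reach is unclear. The eCRF parameters for these events are not in the documents and might contain an onset criterion. This is a reason to state the rule in the SAP.

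**Conclusion.** The concern holds in limited form. An ever/never cardiovascular row is uninformative by design. The other rows mix existing with new dysfunction, so an arm difference in new onset shrinks by the factor (1 − entry prevalence). For renal events at about 50% this halves a 10-point difference to 5 points and lowers power from about 80% to 52%. For the remaining four categories the size is unknown.

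The 100% cardiovascular figure and the about-half renal figure come from the protocol. The 30% and 40% onset rates, and every other entry prevalence in the table, are illustrations. The result also assumes one ever/never count per patient over follow-up, which is the plain reading of a frequency analysis but is not spelled out. The SAP's baseline-free SOFA cut adds to the problem, because the protocol's onset measure would have supplied part of what is missing.

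**What to change.** In SAP 6.8.1, add a by-arm table of new or worsened events per organ category relative to baseline:

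- **Unaffected at entry:** count onset, for example the protocol's rise from below 2 to 2 or more in the matching SOFA subscore.
- **Affected at entry:** count a rise or restart fixed in advance. Patients already at subscore 4 cannot rise, so the cardiovascular row needs the restart rule. Restart can occur only in patients who survive and are weaned. Keep all affected patients in the denominator, and do not condition on weaning.
- **Period:** use the daily eCRF data over the same ICU period, up to day 28, in both arms, not the arm-specific recording periods of Protocol 8.3.
- **Presentation:** show the number at risk beside each rate, with deaths alongside or as a competing event. Keep the planned frequency table as a supplement. It also covers items without a SOFA counterpart, such as thrombocytosis.
- **SAP 6.7:** restore the protocol's onset definition of organ failure, or record and justify the change in SAP 6.11.

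The cost is SAP wording and programming. Daily SOFA components, catecholamines, ventilation and renal replacement are already collected under Protocol 7.5. The downside is that a worsening threshold has to be chosen, and this must be done before any by-arm tables are produced.

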8.4 Documentation of adverse events

All AEs will be recorded promptly by the trial centres in the eCRF. Sepsis-related clinical events will be documented in the daily visits section, all others in the AE section of the eCRF.

Events which should not be documented as an AE:

- Medical or surgical interventions (diseases or symptoms that lead to a necessary intervention are documented as an AE)
- Interventions to treat a pre-existing condition that were already planned before consenting to the clinical trial.
- Daily fluctuations in the clinical picture,
- Normal progression of the disease severity of sepsis,
- · Illnesses that existed before consenting to the clinical trial (this will be documented as concomitant disease and not AEs).

Each AE is to be checked to see whether it meets the criteria for an SAE and, if necessary, proceed according to the SAE declaration procedure (see corresponding chapter 8.6).

At the trial centre, care should be taken to ensure that all persons involved in the treatment of participants are adequately informed about the responsibilities in the event of adverse events.

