8.5 Serious adverse event

According to GCP-V § 3 (30), a Serious Adverse Event (SAE) or a Serious Adverse Reaction (SAR) is any adverse event or adverse reaction that is fatal or life-threatening, requires hospitalisation or prolongation of the length of stay, results in permanent or serious disability or disability or invalidity, or results in a congenital anomaly or birth defect. An SAE may also be an AE which, according to the medical assessment of the assessing investigator/deputy/medical member of the trial group, fulfils a comparable criterion.

A serious adverse event must be documented as an AE in the eCRF and reported with the SAE sheet.

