- Total amount of fluid administration in the ICU (individual average amount of fluids given enterally or parentrally, including volume therapy) and total fluid balance in the ICU (individual average difference between daily fluid administration urinary output and other fluid loss): descriptive statistics, especially quartiles.

All secondary endpoints, unless included in the primary analysis model, will be exploratively compared using appropriate parametric and nonparametric tests between treatment groups.

Health economics:

In the context of the ARISS study, a health economic cost-benefit analysis of volume replacement therapy of the ICU stay will be carried out up to a maximum of day 28. The direct costs of colloid, crystalloid and albumin administration will be recorded and the length of stay (first hospitalisation and stay since study participation) evaluated economically to assess whether albumin administration has an effect on hospital costs or not. At the patient level, DEALE (declining exponential approximation of life expectancy) (27) will be applied to calculate patient-specific life expectancy based on mortality rates in the general population and in the disease-specific population. The subsequent cost-effectiveness analysis will yield the cost per year of life for albumin administration. The robustness of the analysis will be checked with one-way and multi-way analyses as well as probabilistic sensitivity analysis.

Analysis of safety parameters:

Frequencies of AEs and SAEs will be analysed using frequency tables. In addition, frequencies of selected AEs (sepsis-related clinical events) will be analysed.

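### Sepsis-explained events can become AEs or SAEs only in the albumin arm, so the by-arm AE and SAE totals are not comparable, with unknown net direction

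*Protocol*

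**What the plan says.** **Entry to the AE database.** Protocol 8.2 lists sepsis death and six organ classes (cardiovascular, respiratory, hepatic, renal, haematological, neurological). Where sepsis plausibly explains such an event, it is "recorded in both groups as sepsis-related clinical events in the daily eCRF visits, but not as AEs". The investigator documents it at the visit and rates a link with the trial drug as possible or not possible. It is entered as an AE "only if the examiner suspects a connection with the administration of the trial drug, which is therefore only possible in the albumin group". On storage, 8.4 says: "Sepsis-related clinical events will be documented in the daily visits section, all others in the AE section of the eCRF".

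**Serious events.** Protocol 8.5: "A serious adverse event must be documented as an AE in the eCRF and reported with the SAE sheet".

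**Drug-specific list.** Protocol 8.2 adds that "the following effects of the trial drug may be substance-specific and must be documented as AE". The list includes fever, hypervolaemia and pulmonary oedema.

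**Recording window.** Under Protocol 8.3, AEs and sepsis-related events are recorded until 24 h after the last dose in the albumin arm. In the control arm they are recorded until day 28, or until ICU discharge if earlier.

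**Analysis.** Protocol 11.3.2: "Frequencies of AEs and SAEs will be analysed using frequency tables". SAP 6.8.1: "All AEs and serious AEs will be presented by incidence analysis of the pre-specified categories". SAP 6.2 has every analysis done by treatment group. SAP 6.8.1 also plans a frequency table of sepsis-related events by organ category, and a separate display of those entered in the AE database as possibly related to study medication. It does not say that the latter leave the tables of all AEs and SAEs.

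**The concern.** The same sepsis-explained renal failure can be an AE, and an SAE if serious, in an albumin patient, and cannot be one in a control. The step between the two is a causality judgement by an investigator who knows the allocation; Protocol 11.2 states that blinding is not possible. The by-arm AE and SAE totals therefore count different things in the two arms.

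This matters because Protocol 3.2 lists the occurrence of AEs and SAEs among the secondary endpoints. A reader of the by-arm totals cannot tell a harm of albumin from the effect of the entry rule. The rule also differs from the window problem in 8.3: it operates even on days when both arms are being recorded.

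**Working it through.** The documents give no AE or SAE rate and no rate of suspected causality, so there is no figure of the plan to reproduce. The rule can be read directly; its size can only be illustrated.

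**Step 1: follow one event through the rules.** Take a renal failure judged explainable by sepsis.

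| Step | Albumin arm | Control arm |
|---|---|---|
| Daily-visit form (8.2) | recorded | recorded |
| Entered as AE (8.2) | if a link with the trial drug is suspected | not possible |
| Entered as SAE (8.5) | if also serious | not possible |
| Counted among all AEs/SAEs (SAP 6.8.1, 6.2) | yes, if entered | no |
| Sepsis-event table (SAP 6.8.1) | yes | yes |

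An event judged not explained by sepsis goes to the AE section in either arm.

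**Step 2: the entry rule alone, equal windows.** Assume no true difference, a background *b* = 20% of patients with another AE in each arm, and a share *p* of albumin patients with at least one sepsis-type event entered through suspected causality, independent of the background. Then

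albumin total = 1 − (1 − b)(1 − p).

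- p = 5%: 1 − 0.80 × 0.95 = 24%, against 20% in control.
- p = 10%: 1 − 0.80 × 0.90 = 28%, against 20%.

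With 831 randomised per arm (Protocol 1.1), p is 831 × 0.05 ≈ 42 or 831 × 0.10 ≈ 83 albumin patients with an entry of this kind, against 0 controls by rule.

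**Step 3: add the recording window.** Under Protocol 6.3.2 no dose is given while serum albumin is at or above 30 g/l, so the last dose, and with it recording, may precede ICU discharge. Let *w* be the albumin window as a fraction of the control window, with a constant hazard for background AEs:

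albumin total = 1 − (1 − b)^w × (1 − p).

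With b = 20%, 0.80^0.75 = 0.846 and 0.80^0.5 = 0.894. The last column replaces p by p × w, for the case where sepsis-type entries are also lost in proportion to the window.

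| w | p | Control | Albumin, p fixed | Albumin, p × w |
|---|---|---|---|---|
| 1 | 5% | 20% | 24.0% | 24.0% |
| 1 | 10% | 20% | 28.0% | 28.0% |
| 0.75 | 5% | 20% | 19.6% | 18.6% |
| 0.75 | 10% | 20% | 23.9% | 21.8% |
| 0.5 | 5% | 20% | 15.0% | 12.8% |
| 0.5 | 10% | 20% | 19.5% | 15.0% |

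The sign changes within this range. The values of b, p and w are all assumptions.

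**Step 4: remove the flagged entries and leave 8.3 alone.** With p = 0, albumin shows 1 − 0.846 = 15.4% at w = 0.75 and 1 − 0.894 = 10.6% at w = 0.5, against 20%. Removal on its own leaves only the window bias, which favours albumin.

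**The case against.** The strongest reply is that the plan already holds the answer. Sepsis-related events are collected in both arms whatever the causality call, and SAP 6.8.1 tabulates them by organ category. AE entries possibly related to study medication are shown separately, so a reader can identify them. Selective AE recording is deliberate: Protocol 8.2 explains it and cites earlier sepsis trials that used it. No significance test on AEs is specified.

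Most of this stands. The safety information is not lost, the sepsis-event table is untouched by the entry rule, and selective recording itself is not at issue. What remains is that the AE and SAE totals are still tabulated by arm with the one-sided entries inside them. The sepsis-event table is also still exposed to the unequal window, because 8.3 applies to those events too.

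Three stronger readings are tempting, and the documents do not support them.

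- A reader might infer that the totals are inflated against albumin, so that equal true rates must show an excess. The 8.3 window can offset or reverse that.
- A reader might infer that no renal, respiratory or hepatic event in a control can be an AE. The restriction covers only events judged explainable by sepsis; 8.2 says that AEs are assessed in controls.
- A reader might infer that fever or pulmonary oedema in a control goes unrecorded as an AE. The list is mandatory and reads naturally as overriding the sepsis exclusion. Describing its items as effects of the trial drug leaves some doubt, but that is a matter of wording.

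**Conclusion.** The point holds in a limited form. AE and SAE ascertainment differs by arm by rule, and the planned by-arm totals carry that difference. The entry rule alone can only add to albumin; the window can subtract. The totals are therefore not comparable, and the direction of the net error is unknown.

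That conclusion rests on the text of Protocol 8.2, 8.3 and 8.5 and SAP 6.2 and 6.8.1, not on any assumed rate. The size cannot be estimated from the documents. The entry rule's contribution of 4 or 8 percentage points depends on the assumed 20% background, 5% or 10% entry through suspected causality, independence and equal windows. The primary endpoint is not affected. The plan should be changed, and the remedy is cheap.

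**What to change.** **SAP 6.8.1**

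1. Flag each sepsis-type event entered as an AE because of suspected causality.
2. Make the main between-arm safety comparison on one definition: sepsis-related events from the daily-visit form pooled with AEs, whatever the causality call, each event counted once.
3. Use a recording window common to both arms. Controls have no last dose, so their data cannot be cut to match the albumin rule; a common window needs the same end of recording for both arms in Protocol 8.3. Protocol 7.5 already schedules ICU visits to day 28 for both arms. Failing that, give exposure-adjusted rates per recorded day. These assume a stable hazard, so show them within the SAP's existing time bands.
4. Show AE and SAE totals with and without the flagged entries, and list the flagged entries in full for albumin. Do not simply drop them: that would remove suspected drug-related events from the albumin total and leave the window bias standing (Step 4).

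**Protocol 8.2 and the eCRF guide**

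5. State that a flagged event also stays in the daily-visit form. Section 8.2 implies this; 8.4 leaves it open.
6. State that the list of events that must be documented as AEs applies in both arms whatever the suspected cause.

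**Cost.** One dataset flag, one more table and a few sentences. Aligning 8.3 would add some recording in the albumin arm and need a protocol change; the exposure-adjusted alternative avoids that. Expedited reporting is unchanged.
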